The majority of PONV interventions in use in current clinical practice reduce the risk by approximately 20%. This reduction is additive when multiple interventions are used. Assuming a 37% incidence of PDNV based on previous literature, to be powered to find a 20% reduction in risk from baseline the study must include 140 patients.

d) Study Timelines

Patients who consent to and are scheduled to undergo ambulatory surgery at Mount Sinai will be invited by their physician to participate in the study prior to the scheduled date of surgery at their routine preoperative visit. If a patient expresses interest in the study after viewing the recruitment flyer, arrangement will be made for an investigator to meet with the patient in clinic prior to the scheduled surgery to explain the study, screen the patient for eligibility, and obtain consent if appropriate. Patients who are consented will be randomized prior to their planned surgery. They will be followed for postoperative nausea and vomiting for 24 hours after discharge by telephone call on post-operative day one.

	Protocol Title:	Olanzapine for the treatment of Post-Discharge Nausea and Vomiting after Ambulatory Surgery
	Principal Investigator Name/Contact Info:	[name] [contact]
	Primary Contact Name/Contact Info:	[name] [contact] [name] [contact]
	Date Revised:	1/31/2018
	Study Number:	GCO#15-1297; HSM# 15-00501

Based on the enrollment within the first year of the study, we expect to have 20-30 patients complete the study per year. Assuming that enrollment continues at the current pace, it will take approximately five years to enroll the necessary 140 patients. As patients only need to be followed for 24 hours after discharge to be assessed for all primary and secondary endpoints, we estimate the study will be complete within 2 weeks of final patient enrollment.

e) Study Endpoints

Primary Objective: Compare the rate of post-discharge retching/vomiting or nausea in patients who receive olanzapine versus placebo.

Secondary Objectives:

- i) Measure the rate of post-discharge retching/vomiting in patients who receive olanzapine versus placebo.
- ii) Measure the rate of post-discharge nausea in patients who receive olanzapine versus placebo.
- iii) Measure the severity of post-discharge nausea in patients who receive olanzapine versus placebo using an 11-point Likert scale.

f) Procedures Involved in the Human Research

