Subjects who consent to and are scheduled for ambulatory surgery under general anesthesia will be invited to participate in the study during a routine preoperative visit prior to the day of surgery by a study investigator. The details of the study will be reviewed and written informed consent will be obtained. Additionally, a flyer describing the study will be displayed at the two participating clinic locations to advertise the study to potential participants. The flyer will instruct interested patients to discuss the study with their gynecologist, or to contact the principal investigator directly. If a patient tells their physician that they are willing to participate, a study investigator will describe the study in detail, answer questions, confirm participant understanding, and provide the written informed consent form for review. Patients who have agreed to participate will have a 12-lead electrocardiogram (EKG) obtained in pre-surgical testing. Alternatively, if an EKG is not obtained prior to the day of surgery, it will be performed the same day in the assessment area prior

	Protocol Title:	Olanzapine for the treatment of Post-Discharge Nausea and Vomiting after Ambulatory Surgery
	Principal Investigator Name/Contact Info:	[name] [contact]
	Primary Contact Name/Contact Info:	[name] [contact] [name] [contact]
	Date Revised:	1/31/2018
	Study Number:	GCO#15-1297; HSM# 15-00501

to surgery. Patient's with a QTc > 450 ms using the Fridericia formula will be excluded.

Subjects will be counseled verbally to avoid alcohol, benzodiazepines, and motor vehicle driving for 24 hours following discharge.

The name and date of surgery of the consenting patient will be given to the Investigational Drug Service of the Mount Sinai Pharmacy for randomization and preparation of the medication. On the day of surgery, an investigator will pick up the medication from the pharmacy for the individual subject, and have the subject take the medication with a small sip of water in the preoperative holding area within one hour prior to entering the operating room. In addition, the patient will be provided with a standardized diary to record episodes of vomiting for the first 24 hours after discharge and will be provided with verbal and written instructions for completing the diary (appendix 1). Subjects will be asked for a preferred contact number for the postoperative phone call and permission to leave a voicemail will be requested.

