Upon entering the operating room, after application of standard monitors, midazolam 2 mg will be administered for anxiolysis. If endotracheal intubation is indicated, general anesthesia will be induced using fentanyl 3-5 mcg/kg and propofol 1.5-2.5 mg/kg and muscle relaxation achieved with succinylcholine 1-2 mg/kg or rocuronium 0.6 mg/kg, at the discretion of the attending anesthesiologist. Rocuronium will be administered as needed to maintain muscle relaxation during the case. If a laryngeal mask airway is to be used rather than an endotracheal tube, anesthesia will be induced with propofol 1.5-2.5 mg/kg. Regardless of method of airway management, anesthesia will be maintained with sevoflurane at concentrations deemed appropriate by the anesthesia provider based on intraoperative hemodynamic and respiratory monitoring. Additional doses fentanyl will be administered also as deemed appropriate by the anesthesia provider based on intraoperative hemodynamic and respiratory monitoring. All patients will receive dexamethasone 8 mg immediately following induction, and ondansetron 4 mg and ketorolac 30mg approximately 30 minutes prior to emergence from anesthesia unless there is a specific contraindication. Intubated patients will receive neuromuscular blockade reversal with neostigmine 0.4-0.7 mg/kg prior to tracheal extubation.

	Protocol Title:	Olanzapine for the treatment of Post-Discharge Nausea and Vomiting after Ambulatory Surgery
	Principal Investigator Name/Contact Info:	[name] [contact]
	Primary Contact Name/Contact Info:	[name] [contact] [name] [contact]
	Date Revised:	1/31/2018
	Study Number:	GCO#15-1297; HSM# 15-00501

In the PACU, as needed ondansetron will be ordered as per the department standard orderset, (ondansetron 4 mg intravenous every 4 hours). However, the standard prochlorperazine 10 mg intravenous once will be removed from the orderset to reduce the risk of neuroleptic malignant syndrome or extrapyramidal symptoms when administered in combination with olanzapine. The patients' experience of nausea and/or vomiting will be assessed at 30, 60, and 120 minutes after surgery by trained study personnel. PACU EPIC records will also be audited to record the need for rescue antiemetic medications.

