Prior to discharge from the PACU, subjects will be assessed for signs of orthostatic hypotension (a decrease of 20 mmHg in systolic blood pressure or 10 mmHg in diastolic blood pressure upon standing). Patients who meet the criteria for orthostatic hypotension will be evaluated and treated with intravenous fluid administration. Upon discharge, patients who had symptoms of orthostatic hypotension will be instructed to ambulate with assistance for the first 24 hours after discharge.

Information entered into the subjects' diary will be obtained during a telephone interview on the afternoon or evening of the first day following surgery. At this time investigators will also screen for adverse events.

Relevant preoperative, intraoperative, and postoperative data will be obtained from the anesthesia record, the EPIC electronic medical record, and the telephone interviews and collected on standardized forms by trained study personnel.

Data to be collected:

Age
BMI
ASA status
Smoking status
History of PONV
History of motion sickness
Total intraoperative fentanyl (mcg)
Total intraoperative propofol (mg)
Total intraoperative rocuronium (mg)
Total intraoperative neostigmine (mg)
Total intraoperative Sevoflurane
Duration of surgery
Total fentanyl dose in PACU (mcg)

	Protocol Title:	Olanzapine for the treatment of Post-Discharge Nausea and Vomiting after Ambulatory Surgery
	Principal Investigator Name/Contact Info:	[name] [contact]
	Primary Contact Name/Contact Info:	[name] [contact] [name] [contact]
	Date Revised:	1/31/2018
	Study Number:	GCO#15-1297; HSM# 15-00501

Total oxycodone dose in PACU (mg)
Rescue antiemetics in PACU (yes/no)
Ondansetron total dose (mg)
Length of PACU stay (minutes)
Vomiting in PACU (#episodes at least 1 min apart)
Nausea in PACU (highest number reported on 11 point Likert scale)
Post-discharge vomiting (#episodes at least 1 minute apart)
Post-discharge nausea (highest number reported on 11 point Likert scale)

g) Specimen Banking

N/A

h) Data Management and Confidentiality

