[name] and [name] are board certified anesthesiologists with expertise in the perioperative management of patients. All subjects will be called on post-operative day one by a study investigator. In addition to the routine post-operative day one phone call to the patient, all participants will receive instructions and a business card in order to have a point of contact to report a potential adverse event at any time during or after the study period. They will also be specifically informed that they should receive emergency department care for any signs and symptoms of hypotension. Patients who will not have anyone present at home after discharge will receive a same-day follow-up phone call from the study team to screen for adverse events.

The study remains blinded during the second year of enrollment and no interim analysis of efficacy has been performed. No adverse events have been reported by any study participants.

All adverse events will be recorded by the research team in a non-anonymized fashion and reported directly to the Mount Sinai Institutional Review Board.

The study team will report the following to the Institutional Review Board and FDA within 5 business days of when they became aware of the event:

Any event that, in the principal investigator's opinion, is unexpected and at least probably related to the study.

Any event that is expected but occurring with greater frequency/intensity will be reported to the Institutional Review Board and FDA within 5 business days.

	Protocol Title:	Olanzapine for the treatment of Post-Discharge Nausea and Vomiting after Ambulatory Surgery
	Principal Investigator Name/Contact Info:	[name] [contact]
	Primary Contact Name/Contact Info:	[name] [contact] [name] [contact]
	Date Revised:	1/31/2018
	Study Number:	GCO#15-1297; HSM# 15-00501

The study team will report the following to the IRB and FDA on an annual basis:

All expected adverse events

The principal investigator will not enroll any new patients until the IRB has reviewed and responded to the report. The study team will continue to follow patients who are already enrolled.

Enrollment will continue once the IRB approves.

j) Withdrawal of Subjects

Patients may be withdrawn from the study without their consent if their eligibility changes from the time of initial consent to the start of surgery or, if in the opinion of the investigator, they are not appropriate for olanzapine administration.

6) Risks to Subjects

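### The day-1 call that reads out the nausea and vomiting endpoints is set by clock time, not by hours since discharge, so it can fall before the 24-hour window closes

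*Combined protocol and SAP*

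**What the plan says.** Section 5) d), Study Timelines, sets the length of follow-up and the day of the call: "They will be followed for postoperative nausea and vomiting for 24 hours after discharge by telephone call on post-operative day one". The same section ties the endpoints to that period: "As patients only need to be followed for 24 hours after discharge to be assessed for all primary and secondary endpoints". Section 5) f) gives each patient a diary to "record episodes of vomiting for the first 24 hours after discharge".

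Later in section 5) f), the diary information is to be obtained by telephone "on the afternoon or evening of the first day following surgery. At this time investigators will also screen for adverse events". The safety text before section 5) j) repeats the day but gives no hour: "All subjects will be called on post-operative day one by a study investigator".

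The available text sets no minimum interval between discharge and call, and no second call to complete the period. The list of data to be collected in section 5) f) includes PACU stay in minutes, but neither the clock time of discharge nor the time of the call.

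**The concern.** The endpoint is defined by hours since discharge, while its read-out is scheduled by time of day. The two agree only if the call comes no earlier in the day than the discharge did. When it comes earlier, the last hours of the window are unobserved, and the available text gives no route for diary entries made after the call.

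At stake is whether the primary endpoint (any nausea, retching or vomiting after discharge) is observed over the stated period in every patient. Early calls would shorten that period by a different amount in each patient and lower the event count. The trial is aimed at delayed symptoms, and section 2 argues for olanzapine partly from its 21 to 54 hour half-life, so the late hours are of interest.

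**Working it through.** **Inputs from the protocol.** A 24-hour window after discharge (5) d) and 5) f)); a call in the afternoon or evening of day 1 (5) f)); a 37% baseline rate, a 20% reduction and 140 patients (5) c)).

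**Inputs assumed.** All clock times, the timing of first symptoms, equal allocation (70 per arm), an absolute 20-point reduction (37% to 17%), and a two-sided 5% test. The protocol states none of these.

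**Step 1: hours covered.** With D the clock hour of discharge and C the clock hour of the call on the next day,

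hours covered = 24 + C − D.

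The protocol's 24 hours are met exactly when C = D and exceeded when C > D. A call at C < D falls short:

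| Discharge | Call 13:00 | Call 15:00 | Call 18:00 |
|---|---|---|---|
| 15:00 | 22 h | 24 h | 27 h |
| 17:00 | 20 h | 22 h | 25 h |
| 19:00 | 18 h | 20 h | 23 h |

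Section 1 words the research question as 24 hours after surgery. On that anchor, with discharge 2 hours after surgery, the 17:00 discharge and 13:00 call cover 22 hours.

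**Step 2: can afternoon discharge occur?** Nausea is "assessed at 30, 60, and 120 minutes after surgery by trained study personnel". If those assessments are completed before discharge, surgery ending after 10:00 means discharge after 12:00, and a call at noon is then early.

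**Step 3: how often, under assumed times.** Take D and C as uniform and independent. The chance of an early call is the average over D of P(C < D). For discharge 12:00–19:00 and calls 12:00–20:00 this is the mean of (D − 12)/8, or 3.5/8 = 0.4375. For calls 12:00–17:00 it is (2.5 + 2)/7 = 0.643. For calls 17:00–20:00 it is 0.667/7 = 0.095.

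**Step 4: events missed.** With uniform onset over 24 hours, the share of first onsets missed is the mean shortfall over all patients divided by 24. With early-weighted onset (half of the remaining onsets every 6 hours, scaled to 24 hours), it is the average of 1 − (1 − 2^(−t/6))/(1 − 2^(−4)), where t is the hours covered.

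| Discharge | Calls | Early | Mean shortfall if early | Missed, uniform | Missed, early-weighted |
|---|---|---|---|---|---|
| 12–19 | 12–20 | 44% | 2.3 h | 4.3% | 1.0% |
| 12–19 | 12–17 | 64% | 2.5 h | 6.7% | 1.5% |
| 12–19 | 17–20 | 10% | 0.7 h | 0.3% | 0.1% |
| 11–17 | 12–20 | 26% | 1.7 h | 1.8% | 0.4% |
| 11–17 | 17–20 | 0% | – | 0% | 0% |

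In the worst row, 0.37 × (1 − 0.0665) = 0.345.

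**Step 5: power.** The pooled-variance test has power Φ{[|p1 − p2|√n − 1.96√(2p̄(1 − p̄))] / √[p1(1 − p1) + p2(1 − p2)]}. With n = 70, p1 = 0.37, p2 = 0.17 and p̄ = 0.27, this is Φ{(1.673 − 1.231)/0.612} = 76.5%. Reducing both rates by 6.65% (to 0.345 and 0.159) gives 72.5%. In the first row of the table, power is 74.0% with uniform onset and 76.0% with early-weighted onset. With evening calls it is at least 76.4%.

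**The case against.** The best defense is that section 5) d) already states the duration. On that reading, section 5) f) only names the part of the day, and a 13:00 call after a 17:00 discharge breaks the protocol rather than following it. An evening call would usually satisfy both sections. This shows that the intent is clear. It does not remove the gap: the person making the call has a clock-time rule and, in the available text, no instruction to wait.

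A second objection is that the frequencies are assumptions. This stands in full. The 44% and 64% figures require call times chosen without regard to discharge. The 72.5% power figure also needs afternoon-only calls, dropping the evening option that the protocol offers, together with uniform onset. The protocol supports neither condition in particular.

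A third is that the diary (appendix 1), the standardized forms and part of section 5 before j) are not in the available text. A call time may be recorded on the forms, and discharge time may be recoverable from the electronic record. So one can say only that call time is not a listed item, not that early read-outs could never be traced.

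A reader might also infer that the adverse-event screen closes before a 24-hour safety window, since it shares the call and patients are told to "avoid alcohol, benzodiazepines, and motor vehicle driving for 24 hours following discharge" and, after orthostatic symptoms, are "instructed to ambulate with assistance for the first 24 hours after discharge". The documents do not support that inference. Those are precautions, not surveillance periods, and no 24-hour adverse-event window is stated. The safety text before section 5) j) also provides a contact card usable at any time, advice to seek emergency care for signs of hypotension, and a same-day call for patients with nobody at home.

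**Conclusion.** The point holds for the nausea and vomiting endpoints. A call that complies with section 5) f) can read the primary endpoint out before the 24 hours of section 5) d) have passed, by 4 hours in the 17:00 and 13:00 example. That follows from the text and needs no assumption beyond an afternoon discharge.

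How many patients are affected cannot be known from the documents; 0% to 64% is a range of illustrations, not an estimate. Across the same cases, 0% to 6.7% of first-onset events would be missed, and power would be between 72.5% and 76.5%.

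A reader might infer a bias toward one arm. The documents give no ground for it: the trial is blinded, so the hours lost should be similar in both arms. Equal loss of events further assumes that symptoms begin at similar times in both arms, as the calculation does. A later call would extend the adverse-event screen only incidentally. This is a cheap improvement to endpoint ascertainment, not a threat to the trial's validity.

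**What to change.** In section 5) f), require the call at or after 24 hours from the recorded discharge time. For most afternoon discharges this is the evening slot already allowed. If a patient is reached sooner, make one brief second call for the remaining hours.

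After a late discharge (beyond about 20:00, if evening calls stop then), allow a next-morning call. That falls on day two, so section 5) d) and the safety text before section 5) j) must be amended as well, since both name post-operative day one. Changing section 5) f) alone would create a new inconsistency.

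Add discharge time and call time to the list of data. For patients already enrolled, keep the planned analysis and report how many were called before 24 hours, where call times were noted.

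The cost is short wording changes in three places, two form fields and a minor IRB amendment. The downside is more evening calls, a few second or next-morning calls, and possibly slightly lower reach. The change is still worth making: at 20 to 30 completers a year, even two full years give 40 to 60 patients, leaving 80 to 100 of the 140 to come.

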[name] and [name] are board certified anesthesiologists with expertise in the perioperative management of patients. All subjects will be called on post-operative day one by a study investigator. In addition to the routine post-operative day one phone call to the patient, all participants will receive instructions and a business card in order to have a point of contact to report a potential adverse event at any time during or after the study period. They will also be specifically informed that they should receive emergency department care for any signs and symptoms of hypotension. Patients who will not have anyone present at home after discharge will receive a same-day follow-up phone call from the study team to screen for adverse events.

The study remains blinded during the second year of enrollment and no interim analysis of efficacy has been performed. No adverse events have been reported by any study participants.

All adverse events will be recorded by the research team in a non-anonymized fashion and reported directly to the Mount Sinai Institutional Review Board.

The study team will report the following to the Institutional Review Board and FDA within 5 business days of when they became aware of the event:

Any event that, in the principal investigator's opinion, is unexpected and at least probably related to the study.

Any event that is expected but occurring with greater frequency/intensity will be reported to the Institutional Review Board and FDA within 5 business days.

	Protocol Title:	Olanzapine for the treatment of Post-Discharge Nausea and Vomiting after Ambulatory Surgery
	Principal Investigator Name/Contact Info:	[name] [contact]
	Primary Contact Name/Contact Info:	[name] [contact] [name] [contact]
	Date Revised:	1/31/2018
	Study Number:	GCO#15-1297; HSM# 15-00501

The study team will report the following to the IRB and FDA on an annual basis:

All expected adverse events

The principal investigator will not enroll any new patients until the IRB has reviewed and responded to the report. The study team will continue to follow patients who are already enrolled.

Enrollment will continue once the IRB approves.

j) Withdrawal of Subjects

Patients may be withdrawn from the study without their consent if their eligibility changes from the time of initial consent to the start of surgery or, if in the opinion of the investigator, they are not appropriate for olanzapine administration.

6) Risks to Subjects

A single dose of 10 mg of olanzapine is expected to be safe with minimal risks to subjects based on multiple prior studies of olanzapine in chemotherapy-induced nausea and vomiting. The following risks of olanzapine have been described based on chronic use:

Likely (>10%)

Weight gain, dose dependent (5-40%)

Hypertriglyceridemia (\leq 39%)

Hypercholesterolemia (\leq 39%)

Somnolence, dose dependent (6-39%)

Extrapyramidal symptoms (EPS), dose dependent (15-32%)

Xerostomia (9-22%)

Weakness (2-20%)

Dizziness (4-18%)

	Protocol Title:	Olanzapine for the treatment of Post-Discharge Nausea and Vomiting after Ambulatory Surgery
	Principal Investigator Name/Contact Info:	[name] [contact]
	Primary Contact Name/Contact Info:	[name] [contact] [name] [contact]
	Date Revised:	1/31/2018
	Study Number:	GCO#15-1297; HSM# 15-00501

Accidental injury (12%)

Insomnia (12%)

Elevated alanine aminotransferase (ALT) level (5-12%)

Constipation (9-11%)

Dyspepsia (7-11%)

Hyperprolactinemia (30%)

Hyperglycemia (12.8%)

Less Likely (1-10%)

Hypotension (2%)

Postural hypotension (1%)

Tremor (1%)

Asthenia (2%)

Akathisia reactions (2%)

Parkinsonism reactions (4%)

Rare but Serious (<1%)

Syncope

Sudden cardiac death

Hyperglycemia

Diabetic coma with ketoacidosis

Diabetic ketoacidosis

Acute hemorrhagic pancreatitis

Venous thromboembolism

Immune hypersensitivity reaction

Cerebrovascular disease

Seizure, status epilepticus

	Protocol Title:	Olanzapine for the treatment of Post-Discharge Nausea and Vomiting after Ambulatory Surgery
	Principal Investigator Name/Contact Info:	[name] [contact]
	Primary Contact Name/Contact Info:	[name] [contact] [name] [contact]
	Date Revised:	1/31/2018
	Study Number:	GCO#15-1297; HSM# 15-00501

Suicidal intent

Pulmonary embolism

Death

Neuroleptic malignant syndrome (NMS)

Tardive dyskinesia

Drug Reaction with Eosinophilia and Systemic Symptoms (DRESS)

Specifically, a trial comparing olanzapine versus aprepitant for prevention of CINV found no difference in scores between groups in a multi-symptom patient-reported outcome measure (MD Anderson Symptom Inventory (MDASI)), including drowsiness and fatigue.¹³ A trial examining the effectiveness of olanzapine for treatment of breakthrough CINV similarly found no difference between groups in MDASI scores.¹⁴ Another study comparing olanzapine with 5-hydroxytryptamine 3 (5-HT₃) receptor antagonists for prevention of CINV found significant improvements in global health status, emotional functioning, social functioning, fatigue, nausea and vomiting, insomnia and appetite in the olanzapine group. There were no differences in weight, blood lipid or blood glucose levels between groups.¹⁵ These trials support the safety and tolerability of short-term use of olanzapine.

Unlike the cancer patients receiving olanzapine for the prevention or treatment of CINV, patients in this study will be receiving general anesthesia and several other central nervous system depressing (CNS) medications, including intraoperative midazolam and fentanyl, and postoperative oxycodone. The combination of olanzapine and these medications may increase the risk of adverse events not seen in the patients studied for CINV. These risks include sedation, respiratory depression, extrapyramidal symptoms, orthostatic hypotension and cardiac rhythm abnormalities

7) Provisions for Research Related Injury

Subjects will be monitored during surgery and during recovery from anesthesia. Upon discharge, subjects will be provided with a phone number to call should they have any concerns related to surgery, anesthesia, or the study. If necessary, subjects will be instructed to return to the hospital should any complication requiring medical attention occur.

	Protocol Title:	Olanzapine for the treatment of Post-Discharge Nausea and Vomiting after Ambulatory Surgery
	Principal Investigator Name/Contact Info:	[name] [contact]
	Primary Contact Name/Contact Info:	[name] [contact] [name] [contact]
	Date Revised:	1/31/2018
	Study Number:	GCO#15-1297; HSM# 15-00501

Subjects who are injured as a result of this study will be treated until the resolution of the adverse event and the cost billed to them and/or their insurance carrier. Patients will not be compensated for research related injury.

8) Potential Benefits to Subjects

It is possible that patients who participate in this study and are randomized to receive olanzapine may be less likely to experience post-operative nausea or vomiting or that these symptoms may be less severe.

9) Provisions to Protect the Privacy Interests of Subjects

The de-identified data will be stored on secure, password-protected servers maintained by Mount Sinai Information Technology (IT). Access to the data will only be available to Mount Sinai IT administrators, the primary investigator, and co-investigators. When the de-identified data set are released for analysis, a one-way hash ID will be generated for each record. Only study investigators with access to the full data set will be able to match the hash ID to the original record. All investigators have completed HIPAA training regarding maintaining patient PHI confidentiality.

During preoperative evaluation, subjects will be asked what number they prefer to be contacted at after discharge. They will also be asked whether it is ok for an investigator to leave a message. All messages will be of a general nature and will not contain personal health information. Moreover, post-operative evaluation by phone on the day following surgery is routine practice.

10) Economic Impact on Subjects

There are no costs to subjects for participating in this study. Olanzapine or placebo will be provided to the subjects free of charge. There will be no additional visits or tests related to study participation.

11) Payment to Subjects

There is no payment to subjects

12) Consent Process

Eligible patients will be invited to participate in the study prior to the scheduled date of surgery at their preoperative visit. A study investigator will describe the study in detail, answer questions, confirm understanding, and provide the consent form for review. The voluntary nature of this study will be emphasized, and patients who initially agreed to participate may choose to decline participation on

	Protocol Title:	Olanzapine for the treatment of Post-Discharge Nausea and Vomiting after Ambulatory Surgery
	Principal Investigator Name/Contact Info:	[name] [contact]
	Primary Contact Name/Contact Info:	[name] [contact] [name] [contact]
	Date Revised:	1/31/2018
	Study Number:	GCO#15-1297; HSM# 15-00501

the day of surgery. Participants will be asked about the study to confirm understanding prior to providing written informed consent. Only patients who speak English or Spanish will be enrolled. Spanish-speaking patients will be informed of the details of the study and have all questions answered by a co-investigator who is fluent in both Spanish and English, and will be provided the written consent form in Spanish. SOP HRP-090 will be followed.

13) Process to Document Consent in Writing

Consent will be documented using the standard PPHS consent template.

14) Vulnerable Populations

No vulnerable populations will be included in this study.

15) Multi-Site Human Research (Coordinating Center)

N/A

16) Community-Based Participatory Research

N/A

17) Sharing of Results with Subjects

Results will not be shared with individual subjects. Overall study findings describing the outcome of the study will be published in a peer-reviewed journal.

18) IRB Review History

This is a new IRB application

19) Control of Drugs, Biologics, or Devices

Note: The IDS has its own forms that must be completed and a review process that must be followed before the IDS representative will sign off on Appendix B for submission to the PPHS.

The Investigational Drug Service of the Mount Sinai Pharmacy will handle storage of the study medications. After consent is obtained, the subjects name, medical record, and date of surgery will be given to the research pharmacist for randomization. On the day of surgery, an investigator will obtain the medication from the pharmacy and bring it directly to the subject who will take it immediately under direct supervision of the investigator.

	Protocol Title:	Olanzapine for the treatment of Post-Discharge Nausea and Vomiting after Ambulatory Surgery
	Principal Investigator Name/Contact Info:	[name] [contact]
	Primary Contact Name/Contact Info:	[name] [contact] [name] [contact]
	Date Revised:	1/31/2018
	Study Number:	GCO#15-1297; HSM# 15-00501

References:

